### Project summary

Cerebral Palsy (CP) is the most common motor disability in children born preterm. CP can cause profound disability, lifelong need for extensive care and result in significant economic burden. Ideally interventions should be initiated while at-risk infants are still admitted in the neonatal intensive care unit (NICU), at a stage of rapid brain development where intervention may have an impact on synaptic pruning and brain rewiring. Previous studies indicate that intervention focusing on environmental enrichment and emotional connection between mother and infant can positively impact the neurodevelopmental outcomes of infants born preterm. However, whether this type of interventions can improve the motor outcomes of infants at risk for CP remains unknown. To address this gap in knowledge, we have developed a NICU-based multimodal rehabilitation program (NeoRehab) to support neuromuscular development in preterm infants, This multimodal program, is composed of 6 evidencebased interventions (vocal soothing, scent exchange, comforting touch, kangaroo care, infant massage and physical therapy (PT)) administered in a gestational age (GA) appropriate fashion by a parent. We hypothesize that the NeoRehab program will positively impact short-term motor outcomes in preterm infants at risk for CP. At risk infants (≤32 week's gestation and/or ≤1500 grams birthweight) will be eligible for a pilot randomized controlled trial (RCT) comparing the effects of the NeoRehab program versus usual care on short term motor outcomes (general movements, cranial nerves, posture, movements, tone, and reflexes). The primary outcome is to determine the acceptability, feasibility and fidelity of the program by performing direct observation, weekly interviews and activity log reviews. Secondary short-term developmental outcomes will be measured using the Hammersmith Infant Neurological Examination (HINE) instruments, the general movement assessment (GMA), and the Test of Infant Motor Performance (TIMP) at 3 months postmentrual age (PMA). This study addresses one of the priorities of the National Center for Medical Rehabilitation Research to explore "multimodal rehabilitation approaches that promote plasticity and sensorimotor function". Results from this study will provide the preliminary evidence necessary to design and implement a large, multi-center RCT to test the efficacy of NICU-based rehabilitation programs to improve the motor outcomes of infants born preterm.

# Rationale & Background Information

Significance: CP is an umbrella term used to describe a spectrum of disorders related to movement and motor abnormalities that are non-progressive in nature. CP develops after injury to the developing fetal or infant brain. However, in some cases the underlying pathology remains unclear without a history of periventricular leukomalacia, intraventricular hemorrhage, birth asphyxia or neonatal stroke. The reported incidence and prevalence of CP has varied overtime but has not been mitigated by advances in medical care resulting in increased survival of premature and low birth weight infants. Premature infants are at increased risk of CP with the highest prevalence seen in those born at less than 28 weeks gestation. 

Magnetic resonance imaging (MRI) can predict CP with high probability in severe cases, however not for mild-to-moderate CP, resulting in delayed diagnosis and treatment. As a result, the mean age for diagnosis of CP is 1-2 years of age. As such, treatment algorithms are centered on supportive and corrective care and are typically reserved to pre-discharge and most often post NICU discharge time periods. The NeoRehab program aims to address this gap by introducing intervention early during the NICU stay.

#### Innovation:

The possibility of intervention in the NICU is attractive because the brain is highly plastic and actively developing. Interventions at this stage may have a profound disease modifying impact.  Several investigators have evaluated the impact of early intervention strategies on neurodevelopmental outcomes in preterm infants reporting a positive effect on behavioral problems, social-relatedness, and cognitive and language performance. 

Infant massage represents a form of environmental enrichment that has a positive impact on multiple important outcomes after preterm birth including: improved weight gain, decreased stress and improved neurodevelopmental outcomes. Infant massage can be administered by NICU therapist (UVA has several therapists trained in infant massage) and the feasibility of infant massage by the mother is being actively investigated.

Similarly, early PT in the NICU leads to multiple positive outcomes including: increased bone mineralization and reduced incidence of motor delays in very low birth weight infants. Parent-administered PT has recently been shown to be feasible. Results from a recent RCT indicate that a 10 minute intervention twice a day for 3 weeks, from 34 to 36 weeks' PMA resulted in improved motor performance at 37 weeks' PMA. The intervention was supervised by a PT and was primarily designed to promote postural control, head control, and midline orientation.

Finally, studies have shown that interventions promoting the establishment of emotional connection between infant and mother, such as the Family Nurture Intervention (FNI) strategy, can positively impact neurodevelopmental outcomes at 18 months. The FNI targets infants 26-34 weeks PMA and aims to reduce the effects that abnormal sensory inputs in the NICU have on the developing brain. The program aims to enhance the emotional connection between mothers and their premature infants. Nurture specialists met with mothers on average 6.4 hours per week over the course of the NICU stay and continued until discharge (35-38 weeks' PMA). Elements of the FNI include mother/infant calming sessions with scent cloth exchange, vocal soothing, eye contact, kangaroo care, and family-based support sessions. It can be implemented shortly after birth and incorporates multiple elements of routine NICU care, an important point for implementation

# Study goals and objectives

The goal of this project is to investigate the acceptability, feasibility and fidelity of an innovative NICU rehabilitation program that will include six multimodal, GA appropriate, parent-administered interventions (vocal soothing, scent exchange, comforting touch, kangaroo care, infant massage and physical therapy). We will also determine the effects of this program on short-term motor outcomes using the HINE, the GMA and the TIMP instruments in premature infants (≤32 week's gestation and/or ≤1500 grams birthweight).

AIM 1: Enroll 60 preterm infants (<32 weeks' gestation and/or ≤1500 grams) into a pilot RCT to evaluate the acceptability, feasibility (practicality) and fidelity (adherence, exposure and engagement) of a multimodal GA appropriate rehabilitation program during NICU hospitalization compared to standard of care. We will evaluate:

- Acceptability using recruitment, refusal, retention, and follow-up rates as well as weekly interviews with parental participants
- Feasibility (practicality) using direct observations and weekly interviews with parental participants
- Fidelity (adherence, exposure and engagement) using visitation data, activity logs, direct observations, and weekly interviews.

AIM 2: Examine the effect of a multimodal NICU-based rehabilitation program on short-term motor outcomes (general movements, cranial nerves, posture, movements, tone, and reflexes) of premature infants at risk for CP at discharge from the NICU and at 3 months PMA. We hypothesize that this type of GA appropriate multimodal NICU-based rehabilitation program will positively impact short-term motor outcomes by normalizing general movements and improving TIMP and HINE scores.

#### STUDY DESIGN

Methodology: The design will be a RCT at a single site academic NICU-UVA Hospital in Charlottesville Virginia. Randomization will be stratified by birth weight (< 1000 grams and 1000-1500 grams) using a randomly permuted block design with random block sizes of 2 and 4. The intervention group will receive a novel multisensory, multimodal rehabilitative program, which will incorporate elements from the FNI program (scent exchange, touch, vocal soothing) as well as infant massage and parent-administered physical therapy. The intervention will be adjusted to take into account the infant's developmental stage and physiologic stability (See **Table 1**). Additionally, the intervention focuses heavily on interventions the parent can provide.

[figure not shown]

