#### Inclusion and exclusion criteria:

Infants will be eligible for this study if they meet the following criteria:

- GA at birth: ≤32 weeks gestation and/or birthweight ≤1500 grams
- Infants 7 days or older
- Parental ability to perform the interventions or identified designated surrogate (e.g. grandparent)
- Abnormal writhing GMs defined by the presence of a poor repertoire pattern on 2 consecutive weeks or the presence of a cramped-synchronized pattern on any assessment (see **Figure 1**)

Infants will be excluded from the study if they are clinically unstable (requiring high frequency mechanical ventilation, vasopressor support, need for continuous intravenous pain or sedation medication), if their parents do not speak English or if parental participation is hindered (e.g. incarceration or work/personal related issues).

Figure 1: Intervention algorithm

Intervention (n=30): Parents will be provided oral as well as written (Flip book) and illustrated information about the interventions. Study team members will assist with demonstrating appropriate technique for applying interventions and will use the teach-back method to ensure comprehension and understanding. Interventions will be developmentally tailored to the infant's GA (Table 1) as follows:

1. Modified FNI portion of the bundle includes:

[figure not shown]
- a. Vocal soothing: mothers will be instructed to express their feelings to their infant in their native language using varying intonations
- b. Scent exchange: on initial visit, mothers will receive 2 cloths, 1 to place in her bra and 1 to place under her infant's head. Cloths are subsequently exchanged at each visit.
- c. Comforting touch: mothers will be instructed to use gentle but firm and sustained touch by placing the infant's arms on the chest and placing their hand on top. The other hand will be used to gently contain the infants' feet, lightly drawing the knees towards the chest.
- d. Mother-Kangaroo-Care plus: kangaroo care will be combined with gentle touch, vocal soothing and eye contact as described above.
- 2- Infant massage: mothers will be taught moderate pressure massage by PT
- 3- Parent-administered PT: 10 minutes interventions promoting postural and head control as well as midline orientation will be conducted by the mother is recommended starting at 33 weeks' PMA. The intervention will be monitored by a physical therapist for 3 consecutive sessions and weekly thereafter.

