#### Data management and statistical analysis

IRB approval and informed consent will be obtained prior to the start of the study. Video recorded GMA is standard of care in the NICU for neonates born ≤32 week's gestation and/or ≤1500 grams birthweight. Videos will be reviewed and scored independently by at least 2 of the study investigators. Videos will be scored with only the PMA information available to the investigator at the time of review. Inter-rater and intra-rater agreement will be assessed using Cohen's kappa (kappa) and percentage agreement. In case of

disagreement, the videos will be reviewed by all study members trained in the GMA and a consensus will be obtained.

The UVA NICU admits an average of 112 very low birth weight infants every year among which 83 are born at 32 weeks' gestation or less. We anticipate that, in one year of accrual, there will be approximately 120 infants <32 weeks gestation and/or ≤1500g birth weight. Based on a preliminary assessment of children in the NICU, we expect that 80% of these children will be eligible for the study. Recruitment acceptance rates of previous studies conducted in our NICU range from 30-50% for intervention studies and 80-90% for noninvasive studies. Using an acceptance rate of 80% yields an expected accrual of 70 patients per year. Allowing for 10% dropout, accrual of 33 patients per group (power calculation below) can be completed in 1 year.

Quantitative data will be analyzed using descriptive statistics and content analysis will be performed for qualitative responses. Quantitative data will be analyzed using the newest version of SPSS. Due to the exploratory purpose of the specific aim, descriptive statistics will be computed for all quantitative variables (demographic characteristics, recruitment, refusal, retention, follow up rates, % completion of self-report log and number of visitations per unit log). Frequencies and rates will be calculated for categorical variables and means and standard deviations will be calculated for continuous variables.

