Qualitative analysis will included semi-structured interviews with adult participants as well as direct observations using qualitative description. Qualitative descriptive analysis will provide a comprehensive evaluation of the NICU multimodal rehabilitation program. The textual data from the interviews and observation notes will be analyzed by (1) immersion in the data (2) followed by line by line analysis and data reduction of the textual data through inductive open coding and constant comparative analysis. Tentative categories will be listed with each line of data and identified by "nodes" in the Dedoose software. (3) After line-by-line analysis of the transcripts, categories ("nodes") will be grouped together to form tentative themes.

Repeated measures models will be used to compare HINE and TIMP total scores at the time of discharge and at 3 months PMA between newborns in the standard care group and in the intervention group (NEO rehab program). F-tests based on contrasts will be used to make comparisons at the two specific time points. To approximate the power of the F-test for comparing the groups with respect to the 3-month HINE scores, the results in Romeo et al.(2008) were used. Their study showed that across CP diagnoses, the average 3 –month HINE score was approximately 40 with an estimated standard deviation of 8.8. A score of below 40 is associated with the GMFCS IV and V levels while a score of 40-60 is associated GMFCS levels I and II at 3 months of age. A score ≥ 73 is optimal. With 30 subjects per group, the two-sample t-test has 80% power, with a 2-sided significance level of 5% when the effect of the intervention is to increase HINE scores by 6.5 points. Allowing for 10% dropout, 33 patients per group are required. Similar analyses will be used for the TIMP scores as well as subscales of the HINE. For the GMA assessments, we will tabulate the proportion of children in each group classified as having poor repertoire, cramped/synchronized or chaotic movement abnormalities at each of the followup times. Markov models will be used to assess how the intervention affects the proportions of children transitioning between classifications. For all of the endpoints; this study will provide estimates of variation useful for planning a larger study of the rehabilitation program. Our primary analysis will be done as intention-to-treat.

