The short-term impact of these combined interventions on motor function will be assessed using the HINE, theGMA and the TIMP. These instruments will be administered at time of discharge from the NICU and at 3 months PMA. These instruments used in combination are recommended to be administered to infants before 5 months PMA and provide the most predictive of risk for CP. Instruments will be administered by certified providers and/or therapists. Additionally, demographic characteristics of the sample will be collected using the medical record and include: gender, ethnicity, race, gestational age at birth, birth weight and head circumference, primary diagnosis, neurologic comorbidities, medication management of neurologic comorbidities and neonatal abstinence syndrome, NICU length of stay,

feeding method upon discharge, discharge head circumference, geographical region, and disposition (death or discharge home).

Table 3: Short term developmental outcomes

Instrument	Measurement	Age	Interval
HINE	26 items used to assess cranial nerve function, posture, quality and quantity of movements, muscle tone, and reflexes and reactions). Each item is scored individually 0-3 with a sum score of all individuals ranging from 0-78. Lower the score the poorer the motor function. The HINE allows for identification of early signs of CP and individual items have demonstrated predictive value of motor outcome. Sensitivity 90% for prediction of motor outcome.	2 and 24 months of age	At time of discharge and 3 months PMA
GMA	Writhing stage 1) normal 2) poor repertoire- monotonous and lack complexity 3) cramped-synchronized- appear rigid and are not smooth or fluent in character. 4) chaotic -characterized by abrupt, large amplitude movements involving all limbs. Fidgety stage 1) normal 2) abnormal fidgety movements-absent or abnormal (exaggerated). Cramped-synchronized followed by absent fidgety pattern, have a 98% sensitivity and specificity for prediction of CP	Writing movements birth-9 weeks Fidgety movements 9- 20 weeks	Every 2 weeks during hospitalization and 3 months PMA
TIMP	28 observed items of spontaneous movements and 31 elicited items that assess the child's motor responses scored 0-6. The lower the score the poorer the motor function. The test is sensitive to age-related changes in motor performance ( $r = 0$ .83).	32 weeks to 4 months post term	At time of discharge and 3 months PMA

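### Eligible infants of 32 weeks or less who weigh more than 1500 g belong to neither randomisation stratum, and the HINE and TIMP models name no stratum term

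*Combined protocol and SAP*

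**What the plan says.** **Strata.** The Methodology paragraph under Study Design gives the only stratification rule: "Randomization will be stratified by birth weight (< 1000 grams and 1000-1500 grams) using a randomly permuted block design". Block length varies at random between 2 and 4.

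**Eligibility.** Inclusion and exclusion criteria admit infants on "GA at birth: ≤32 weeks gestation and/or birthweight ≤1500 grams". The Project summary and the Study goals and objectives section join gestation and weight in the same either-or-both way; the Project summary says infants meeting it ("grams birthweight) will be eligible for a pilot randomized controlled trial") can enter the trial.

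**Screening.** Under Data management and statistical analysis, the movement assessment that identifies candidates covers the same infants: "Video recorded GMA is standard of care in the NICU for neonates born", followed by the same gestation-or-weight rule.

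**Counts.** The same section says the unit "admits an average of 112 very low birth weight infants every year" and that one year of accrual should yield "approximately 120 infants <32 weeks gestation and/or ≤1500g birth weight".

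**Model.** "Repeated measures models will be used to compare HINE and TIMP total scores at the time of discharge and at 3 months PMA", with F-tests on contrasts at each time point. No covariate is named and none is ruled out. Birth weight is collected, as Expected outcomes of the study lists "gender, ethnicity, race, gestational age at birth, birth weight and head circumference".

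**The concern.** The two strata together stop at 1500 g, but eligibility does not. When an eligible infant above that weight is consented, the site has two options, and the protocol authorises neither.

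- **Turn the infant away.** This contradicts the eligibility rule and could affect a primary outcome, because Table 2 sets a recruitment target of at least 75%. At the assumed 80% acceptance, losing 8 of 120 would give 0.80 × 112/120 = 74.7%. This is only an illustration: the protocol does not define the denominator, and heavier infants may not meet the other criteria equally often.
- **Choose a list on the spot.** Blocks of 2 and 4 are short, and parents are taught the intervention at the bedside, so allocations become known. A free choice between two such lists is discretion that a pre-specified stratum removes.

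The model question is smaller. When randomisation is stratified on a factor that predicts the outcome, an analysis that ignores the factor remains unbiased but overstates the standard error. What is at stake is precision.

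**Working it through.** **1. The plan's own power figure.** Inputs from Data management and statistical analysis: 30 per group, difference 6.5 HINE points, SD 8.8, two-sided 5%. The standard error is 8.8 × √(2/30) = 2.27 and the noncentrality is 6.5/2.27 = 2.86. The noncentral t distribution on 58 degrees of freedom gives 80.3% power. The stated 80% reproduces and is not in dispute.

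**2. Eligibility against strata.**

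| Infant | Eligible on gestation or weight? | Stratum |
|---|---|---|
| Below 1000 g | Yes | Lower |
| 1000 to 1500 g | Yes | Upper |
| Above 1500 g, 32 weeks or less | Yes | None |
| Above 1500 g, over 32 weeks | No | Not needed |

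The third row is the gap.

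**3. Size of the gap.** Assume that very low birth weight means 1500 g or less, that the two yearly counts are comparable, and that heavier infants meet the other criteria and consent equally often. The excess of the pool over the very low birth weight count is then the group above 1500 g.

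- Pool 120: 120 − 112 = 8 a year; 8/120 = 6.7%; × 60 = 4.0 infants.
- Pool 115: 3/115 × 60 = 1.6 infants.
- Pool 125: 13/125 × 60 = 6.2 infants.
- Even at an assumed share of only 3%, the chance of at least one such infant among 60 is 1 − 0.97^60 = 84%.

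The pool is described with gestation strictly under 32 weeks, whereas the eligibility list says 32 or less. Read literally, heavier infants of exactly 32 weeks would come on top of the 8.

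**4. Effect of leaving the stratum out of the model.** The documents do not say how much HINE variance birth weight explains, so a share R² of 0 to 30% is assumed. One time point is used, as the plan does for its own power.

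- True standard error under stratified allocation: 8.8 × √(1 − R²) × √(2/30).
- Standard error used by the unadjusted test: about 8.8 × √(2/30), so it is too wide by a factor 1/√(1 − R²).
- Type I error, unadjusted: 2 × [1 − Φ(1.96/√(1 − R²))].
- Power, adjusted: noncentral t on 57 degrees of freedom with SD 8.8 × √(1 − R²).
- Power, unadjusted: by simulation (60 infants, permuted blocks of 2 and 4 within two strata, 40% assumed below 1000 g).
- Gap between stratum means: 8.8 × √(R²/(0.4 × 0.6)).

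| R² | Gap between strata (points) | Standard error too wide by | Type I error, unadjusted | Power, unadjusted | Power, adjusted |
|---|---|---|---|---|---|
| 0% | 0 | 0% | 5.0% | 80% | 80.3% |
| 5% | 4.0 | 3% | 4.4% | 81% | 82.3% |
| 10% | 5.7 | 5% | 3.9% | 81% | 84.2% |
| 20% | 8.0 | 12% | 2.8% | 83% | 88.2% |
| 30% | 9.8 | 20% | 1.9% | 84% | 91.9% |

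Simulated type I errors agree with the formula to within about 0.4 percentage points. The last two rows need a gap between strata larger than the planned 6.5-point effect, so they are an upper end.

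**The case against.** The strongest reply is that the upper list is the natural place for a heavier infant. Allocation from it would still be a random permuted-block draw and the comparison would stay valid, so this is an incomplete label rather than a broken design. That is fair as to consequence: no bias is shown. But the protocol does not say the upper list is to be used, and a rule left to the moment is what stratified randomisation is meant to avoid.

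Second, the figures in Study Design and in the eligibility section are not shown, and one of them might contain a rule. This cannot be excluded. Nothing in the text points to one.

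Third, the error might lie in eligibility instead. The stated accrual of 70 a year is closer to 112 × 0.8 × 0.8 = 71.7 than to 120 × 0.8 × 0.8 = 76.8, which would fit a plan limited to 1500 g. The hint is weak. The gestation-or-weight rule appears in several sections, which makes the strata the outlier.

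Fourth, the count of 8 subtracts an observed average from a rounded forecast, and the variance shares are assumed. Both limits stand, so only ranges are given.

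Fifth, the model point concerns secondary outcomes of a pilot whose primary endpoint is feasibility, and unadjusted power never falls below 80% in the table. That is correct, and it is why the point is ranked second.

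**Conclusion.** The concern holds. As written, the strata do not cover every eligible infant, and no text shown says what to do with one above 1500 g. This follows from the wording alone. The number affected is small: about 4 of 60, with a range of roughly 2 to 6, given the meaning of very low birth weight and the comparability of the two yearly counts. The site should nevertheless expect to meet the case.

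The missing stratum term is a gain in precision forgone, not a shortfall against the plan. It makes the HINE and TIMP tests conservative to the extent that birth weight predicts the score, which the documents do not quantify. The change should be made, but neither part undermines the primary feasibility outcomes or the sample size.

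**What to change.** 1. **Strata.** Define them as below 1000 g and 1000 g or more. Every eligible infant then has one stratum, and eligibility and sample size are unchanged. The cost is one line in the randomisation set-up and a slightly wider weight range in the upper stratum. If the sponsor did intend a limit of 1500 g, the eligibility text should be amended everywhere it appears.

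2. **Model.** State that the HINE and TIMP repeated-measures models include the randomisation stratum as a fixed effect; continuous birth weight is an acceptable alternative if one form is chosen in advance. The cost is one degree of freedom. In simulation, power is the same with or without the term (80.2%) when birth weight does not predict the score.

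3. **If enrolment has begun.** The no-cost extension and the project dates suggest this is possible. Changing the strata may then need an amendment. Record which list was used for any infant above 1500 g already randomised, and analyse that infant in the stratum from which the allocation was drawn. The model term can still be specified before the outcome data are analysed.

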Mothers/Fathers whose infants are randomized to the intervention group will be encouraged to be at the bedside and provide the GA appropriate interventions once per day, 5 days per week (5/7).

Table 1: Developmental-Guided NICU based rehabilitation program

	Postmentrual Age (completed weeks)				
Interventions	23-25	26-28	29-32	33-36	≥37
Vocal soothing					
Scent exchange					
Comforting touch					
Kangaroo care plus					
Infant massage					
Parent-administered PT				_	

Standard of care (control group) (n=30): Parents of infants randomized to standard care will continue to be encouraged to touch, hold, and talk to their infants. They are also encouraged to perform kangaroo care based on unit guidelines. All infants in standard care will have a routine physical therapy consult at 28 weeks gestation. The infants will continue to be followed 2-3 times per week for 10-30 minutes per session by PT until discharge from hospitalization. Social work actively engages with parents of infants admitted to the NICU which will include the intervention and standard of care group. Social work provides ongoing parental support and strives to alleviate barriers to visitation. At time of discharge standard care will resume for both groups, which includes a referral to early intervention and a NICU follow up appointment with developmental pediatrics at 3 months PMA. Below is the study schedule.

Self-report activity logs (separately uploaded documents) will be used to monitor the fidelity of the program. Both groups will fill out the log and document what aspects of the program were performed, the date, and duration of the intervention. Weekly interviews will be conducted with parental participants to evaluate the acceptability (satisfaction), feasibility (practicality) and fidelity (engagement) of the program. Weekly interviews will be done at the bedside with parental participants and a research team member to discuss any challenges or barrier to applying the recommended evidence based practice interventions. Examples of interview questions are 1) How are things going? 2) Do you have any questions about the interventions? 3) Are there things that are preventing you from doing the interventions? Additionally, research team members will perform random direct observations of intervention application to further evaluate feasibility and fidelity.

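### The plan has no rule for siblings from a multiple birth, so co-twins can be allocated to different arms although one parent is taught and delivers the programme

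*Combined protocol and SAP*

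**What the plan says.** **Unit of allocation.** AIM 1 (Study goals and objectives) enrols 60 infants. The strata in Study Design are the infant's own birth weight, below 1000 g or 1000–1500 g, and allocation is made "using a randomly permuted block design with random block sizes of 2 and 4". The text below the eligibility criteria speaks of the infant as the randomised unit: "Mothers/Fathers whose infants are randomized to the intervention group will be encouraged to be at the bedside".

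**Eligibility.** Each infant qualifies on its own general movements: "Abnormal writhing GMs defined by the presence of a poor repertoire pattern on 2 consecutive weeks", or a cramped-synchronized pattern at any assessment. The exclusions are clinical instability, and cases "if their parents do not speak English or if parental participation is hindered". Twins, multiples and siblings are mentioned nowhere.

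**Delivery.** Study Design states that "the intervention focuses heavily on interventions the parent can provide". Parents are taught with a flip book, demonstration and teach-back. A designated surrogate may take the parent's place.

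**Control arm.** "Parents of infants randomized to standard care will continue to be encouraged to touch, hold, and talk to their infants". Kangaroo care follows unit guidelines, and a physical therapist sees the infant 2–3 times a week. Scent-cloth exchange, massage by the parent and parent-administered PT are not listed. Both groups complete the activity log.

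**Analysis.** HINE and TIMP totals go into repeated measures models, and "F-tests based on contrasts will be used to make comparisons at the two specific time points". Power is for a two-sample t-test. No family term is named. The primary analysis is by intention to treat.

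**The concern.** A parent who has been taught massage, scent exchange and PT for one twin cannot be expected to withhold them from the other. If the other twin is a control, two things follow.

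- The intention-to-treat contrast shrinks, because the exposed control infant stays in the control arm.
- The primary outcomes lose their separation by arm. Visitation, log completion and weekly interviews (Table 2) all come from the parent, so one family would supply data to both arms. Recruitment and refusal have no stated denominator for a family approached about two infants.

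The protocol also intends the study to supply estimates of variation for planning a larger trial. A diluted difference and an unmodelled sibling correlation would be carried into that planning.

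**Working it through.** **1. The plan's own figure.** Inputs from Data management and statistical analysis: 30 per group, difference 6.5, SD 8.8, two-sided 5%. The noncentrality is 6.5 / (8.8 × √(2/30)) = 6.5 / 2.272 = 2.861 on 58 degrees of freedom, which gives power 80.3%. The stated 80% reproduces.

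**2. Chance that an enrolled pair is split.** The documents do not give the probability of each block size; equal probabilities are assumed, so the mean block length is 3. Adjacent infants inside a block of 2 always differ. Adjacent infants inside a block of 4 differ with probability 2/3 (three such adjacencies). Across a block boundary the probability is 1/2. For consecutive allocations in one stratum:

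(0.5 × 1 + 0.5 × 3 × 2/3 + 1 × 0.5) / 3 = 2.0 / 3 = 0.667

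| Position of the co-twins | P(split) |
|---|---|
| Consecutive, same stratum | 67% (64–70% if the chance of a size-2 block is 0.25–0.75) |
| One infant between | 56% |
| Two between | 53% |
| Three or more between, or different strata | 50% |

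The very first two infants in a stratum are split with probability 0.5 × 1 + 0.5 × 2/3 = 83%, but that is a special case. The working range is 50–67%.

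**3. Dilution.** Let s be the share of infants with an enrolled co-twin (assumed 15–35%), p the split probability (50–67%, step 2) and c the fraction of the effect reaching the control co-twin (assumed 0.5–1). With the SD unchanged, the expected number of exposed controls is 30 × s × p, and the diluted difference is 6.5 × (1 − s × p × c).

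| s | p | c | Exposed controls of 30 | Difference | Power |
|---|---|---|---|---|---|
| 0.15 | 0.50 | 0.5 | 2.3 | 6.26 | 77% |
| 0.15 | 0.667 | 1 | 3.0 | 5.85 | 72% |
| 0.35 | 0.50 | 0.5 | 5.3 | 5.93 | 73% |
| 0.35 | 0.667 | 1 | 7.0 | 4.98 | 58% |

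If only half as many infants have an enrolled co-twin (s = 0.075–0.175) and p = 0.50, power is 79% (c = 0.5) to 73% (c = 1).

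**4. Standard errors.** For pairs, the design effect on the between-arm variance is 1 + s × ICC × [P(same arm) − P(split)]. The ICC is assumed to be 0.3–0.7.

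- Individual allocation, p = 2/3: from 1 − 0.15 × 0.3 / 3 = 0.985 to 1 − 0.35 × 0.7 / 3 = 0.918.
- Individual allocation, p = 1/2: 1.00.
- Siblings kept together: from 1 + 0.15 × 0.3 = 1.045 to 1 + 0.35 × 0.7 = 1.245. Power at 30 per group is then 79–71%.

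**The case against.** The strongest reply is that the documents are silent rather than wrong. No sentence says that twins are randomised separately; that is the natural reading of infant-level wording. The quoted block rule by itself says nothing about siblings. This stands, and the point is therefore put as a missing rule whose absence permits split pairs.

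A reader might go further and infer that co-twins will usually be split. The two-thirds figure needs back-to-back allocation in one stratum. Each infant must qualify on its own movements and clinical stability, so co-twins may enter on different dates, fall in different strata, or not both enter.

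A reader might also infer that control twins are in fact contaminated. The documents show only that they can be. Touch, holding, talking and kangaroo care are already common to both arms, so a full transfer of the effect (c = 1) is an upper bound. The activity logs could reveal crossover, although they would not prevent it.

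Finally, this is a pilot with feasibility as its primary end point, so power for HINE is a secondary matter. That limits the weight of step 3. It does not answer the problem that one parent's data would enter both arms of the primary outcomes, or that the estimates feed the next trial.

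**Conclusion.** The concern holds in this form: infants are the unit, multiples can enter, the parent is the person trained, and neither allocation nor analysis has a sibling rule. Followed as written, about half to two thirds of enrolled pairs would be split. Under the assumed ranges, the HINE difference falls from 6.5 to about 6.3–5.0 points and power from 80% to about 77–58%. The lower end needs every input at its unfavourable extreme, and the loss is smaller if few co-twins both qualify. The share of multiples and the degree of spill-over are assumptions throughout.

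It would be tempting to add that ignoring sibling correlation makes the planned standard errors too small. The check does not support that for individual allocation, where the design effect is 0.92–1.00 and the independence analysis is neutral to slightly conservative. The design effect of 1.05–1.25 arises only once siblings share an arm. It is the price of the remedy, not an error in the current standard errors.

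**What to change.** **Study Design, after the block rule.** *Siblings from a multiple birth are allocated to the same arm. The first eligible sibling is randomised in its own birth-weight stratum; if siblings qualify together, the stratum of the lowest-birthweight one is used. Any sibling who qualifies later takes that arm.*

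**Data management and statistical analysis.** Add a family random effect, or family-clustered standard errors, to the HINE and TIMP models.

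**Expected outcomes, Table 2.** State that recruitment, refusal, visitation and interviews are counted per family.

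**Cost.** A few sentences of text. Arm sizes may be slightly unbalanced. Consent for a sibling who qualifies later is given with the arm already known, so report how many enter this way. At 30 per group, power for HINE would be about 79–71% under the same assumptions. Restoring 80% would take about 30 × 1.045 to 30 × 1.245, that is 32–38 evaluable infants per group. This may overlap with the power lost to dilution, so the case for the change rests on an unbiased contrast and a clean separation of the arms, not on a gain in power.
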